2.6.2 Statistical hypothesis, model, and method of analysis

The primary efficacy endpoint ORR will be estimated, and the exact binomial 95% confidence interval (CI) ([Clopper, Pearson 1934](#)) provided.

Treatment with JDQ443 will be considered to have clinically relevant efficacy if an ORR of [REDACTED] (per RECIST 1.1 by BIRC assessment) is observed with the lower bound of the 95% confidence interval [REDACTED]. The following statistical hypotheses will be tested:

H_0 : ORR [REDACTED] vs. H_1 : ORR [REDACTED]

The tests will be performed based on the exact binomial CI for ORR using a one-sided $\alpha=0.025$ level. The null hypothesis will be rejected if the lower bound of the two-sided 95% exact CI is $\geq 35\%$.

2.6.3 Handling of intercurrent events

The primary analysis will account for different intercurrent events as follows:

1. Discontinuation of study treatment: Tumor assessment data collected after discontinuation of study treatment for any reason will be included to derive BOR (treatment policy strategy).
2. Start of a new anti-neoplastic therapy: If any new anti-neoplastic therapy is initiated, responses documented after the use of new anti-neoplastic therapy will be considered as non-response (composite strategy). Protocol-allowed radiotherapy is exempted.
3. Any public health emergency as declared by local or regional authorities, i.e., pandemic, epidemic or natural disaster: Tumor assessment data collected irrespective of such unforeseen events will be considered for the BOR (treatment policy strategy).

2.6.4 Handling of missing values not related to intercurrent event

The determination of the BOR incorporates missing values including cases of participants with no valid post-baseline assessments.

Confirmed PR or CR reported prior to any additional anticancer therapy will be considered as responses in the calculation of the ORR irrespective of the number of missed assessments before response.

Participants with a BOR of 'Not evaluable' per RECIST 1.1 will be considered as non-responders when estimating ORR. Participants who have disease progression and continue to receive study treatment after progression per RECIST 1.1 by BIRC will qualify for PD at the time of progression and will be counted as PD in the derivation of BOR.

2.6.5 Sensitivity analyses

Not applicable.

2.6.6 Supplementary analyses

2.6.6.1 Supplementary estimands

A supplementary estimand is defined by the same target population, treatment of interest, intercurrent events, and summary measure as for the primary estimand (see [Section 1.2.1](#)). Differently from the primary estimand, the primary variable is the BOR per RECIST 1.1 assessed by the Investigator (local assessment), with responses documented after the use of any new anti-neoplastic therapy (with the exception of protocol-allowed radiotherapy) considered as non-response.

The method of analysis as well as the handling of intercurrent events and missing data will be the same as described in [Section 2.6.2](#), [Section 2.6.3](#), and [Section 2.6.4](#).

A second supplementary estimand is defined by the same primary variable, treatment of interest, intercurrent events, and summary measure as for the primary estimand (see [Section 1.2.1](#)). Differently from the primary estimand, the target population will be participants with both presence of a KRAS G12C mutation and PD-L1 expression < 1% centrally confirmed in tumor tissue, i.e. subgroup 2a.

The method of analysis as well as the handling of intercurrent events and missing data will be the same as described in [Section 2.6.2](#), [Section 2.6.3](#), and [Section 2.6.4](#).

2.6.6.2 Other supplementary analyses

A subgroup analysis of ORR by central and local investigator review will be prepared for cohort A for the subgroups 4a to 4h.

2.7 Analyses supporting key secondary objectives

The key secondary clinical questions of interest and the corresponding estimands are defined in [Section 1.2.2](#).

The key secondary objectives are to assess the antitumor activity of JDQ443 single-agent as first-line treatment for participants with locally advanced or metastatic NSCLC whose tumors harbor a KRAS G12C mutation, a PD-L1 expression $\geq 1\%$ and an STK11 co-mutation (cohort B), and to evaluate the duration of response (DOR) in both cohorts.

As the two cohorts represent different patient populations, a multiplicity adjustment for the analysis of the primary and first key secondary endpoints is not applicable. For the analysis of the other key secondary endpoints there is also no multiplicity adjustment planned.

The key secondary efficacy endpoints will be assessed using the FAS.

2.7.1 Key secondary endpoints

The key secondary endpoints are ORR in cohort B as well as duration of response in both cohorts (A and B).

ORR by BIRC for cohort B

ORR per RECIST 1.1 by BIRC in cohort B is defined in the same way as specified in [Section 2.6.1](#).

DOT by BIRC for cohort A and cohort B

Duration of response is defined as the duration of time between the date of first documented response (PR or CR) and the date of the first documented radiological progression or death due to any cause. DOT will be evaluated based on the BIRC assessment.

DOT only applies to participants whose best overall response is CR or PR based on tumor response data per BIRC assessment. If a participant has not had an event, DOT will be censored at the date of the last adequate tumor assessment using the censoring rules described in [Table 2-5](#). Participants who never achieved a BOR of CR or PR will be excluded from the analysis.

2.7.2 Statistical hypothesis, model, and method of analysis

ORR by BIRC for cohort B

The ORR in cohort B will be estimated and the estimate as well as the exact binomial 95% CI will be presented.

Treatment with IDQ443 will be considered to have clinically relevant efficacy in cohort B if an ORR of [REDACTED] is observed with the lower bound of the 95% CI [REDACTED]. The following statistical hypotheses will be tested:

H_0 : ORR [REDACTED] vs. H_1 : ORR [REDACTED]

The test will be performed based on the exact binomial CI for ORR using a one-sided $\alpha=0.025$ level. The null hypothesis will be rejected if the lower bound of the two-sided 95% exact CI is $\geq 20\%$.

DOT by BIRC for cohort A and cohort B

The DOT distribution will be estimated using the Kaplan-Meier method, and the Kaplan-Meier curves, medians and 95% confidence intervals of the medians will be presented by cohort.

2.7.3 Handling of intercurrent events

ORR by BIRC for cohort B

The analysis will account for different intercurrent events as follows:

1. Treatment discontinuation for any reason: Tumor assessment data collected irrespective of treatment discontinuation will be included to derive BOR (treatment policy strategy).
2. Start of a new anti-neoplastic therapy: If any new anti-neoplastic therapy is initiated, responses documented after the use of new anti-neoplastic therapy will be considered as non-response (composite strategy). Protocol-allowed radiotherapy is exempted.

3. Any public health emergency as declared by local or regional authorities, i.e., pandemic, epidemic or natural disaster: tumor assessment data collected irrespective of such unforeseen events will be considered for the BOR (treatment policy strategy).

DOR by BIRC for cohort A and cohort B

The analysis will account for different intercurrent events as follows:

1. Treatment discontinuation for any reason: Tumor assessment data collected irrespective of treatment discontinuation will be included to derive DOR (treatment policy strategy).
2. Start of a new anti-neoplastic therapy: If any new anti-neoplastic therapy (with the exception of protocol-allowed radiotherapy) is initiated, progression or death occurring after the use of new anti-neoplastic therapy will not be considered and the DOR will be censored.
3. Any public health emergency as declared by local or regional authorities, i.e., pandemic, epidemic or natural disaster: tumor assessment data collected irrespective of such unforeseen events will be considered for the DOR (treatment policy strategy).

2.7.4 Handling of missing values not related to intercurrent event

ORR by BIRC for cohort B

Participants with no valid post-baseline assessments will be assigned NE and will be included in the BOR derivation.

Confirmed PR or CR reported prior to any additional anticancer therapy will be considered as responses in the calculation of the ORR irrespective of the number of missed assessments before response.

Participants with a BOR of 'Not evaluable' per RECIST 1.1 will be considered as non-responders when estimating ORR. Participants who have disease progression and continue to receive study treatment after progression per RECIST 1.1 by BIRC will qualify for PD at the time of progression and will be counted as PD in the derivation of BOR.

DOR by BIRC for cohort A and cohort B

DOR events will be included in the analysis if they occur after one missing assessment.

Radiological progression or death observed after 2 or more missing tumor assessments will not be included in the derivation of the time to event for DOR, and the observation will be censored at the time of the last adequate tumor assessment prior to the first missing assessment. Participants without a post-baseline tumor assessment (and without death) will be censored at the time of start of study treatment.

The date of last adequate tumor assessment is the date of the last tumor assessment with overall lesion response of CR, PR or SD or non-CR/non-PD before an event or a censoring reason occurred. In this case the last tumor evaluation date at that assessment will be used. If no post-baseline assessments are available (before an event or a censoring reason occurred), the date of start of study treatment will be used.

In particular, DOR will be censored at the last adequate tumor assessment if one of the following occurs: absence of event; the event occurred after two or more missing tumor assessments. The term “missing adequate tumor assessment” is defined as a tumor assessment (TA) not performed or tumor assessment with overall lesion response of “not evaluable (NE)”. The rule to determine the number of missing TAs is based on the time interval between the date of last adequate tumor assessment and the date of an event. If the interval is greater than twice the protocol-specified interval between the TAs and 2 times the protocol-allowed time window around assessments, then the number of missing assessments will be 2 or more.

Refer to [Table 2-5](#) for censoring and event date options and outcomes for DOR. The same principles also apply for PFS.

Table 2-6 Outcome and event/censor dates for DOR and PFS analysis

Situation	Date	Outcome
No baseline assessment	Date of start of treatment*	Censored
Progression or death at or before next scheduled assessment	Date of progression (or death)	Progressed
Progression or death after exactly one missing assessment	Date of progression (or death)	Progressed
Progression or death after two or more missing assessments	Date of last adequate assessment prior to missed assessment	Censored
No progression (or death)	Date of last adequate assessment	Censored
Treatment discontinuation due to “Disease progression” without documented progression, i.e., clinical progression based on investigator claim	Ignore the new anticancer therapy and follow situations above	As per above situations
New anticancer therapy given prior to protocol defined progression	Date of last adequate assessment prior to start of new anticancer therapy	Censored
Death before first PD assessment	Date of death	Progressed

*The rare exception to this is if the participant dies no later than the time of the second scheduled assessment as defined in the protocol in which case this is a PFS event at the date of death

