A further secondary clinical question of interest is: In participants who respond to the JDQ443 monotherapy based on RECIST 1.1 assessed by BIRC, how long does the response to first-line treatment for participants in cohort A or in cohort B last, regardless of study treatment discontinuation and any unforeseen events resulting from a public health emergency?

The justification for this secondary estimand is that it will capture the duration of the treatment effect irrespective of study treatment discontinuation but avoids the confounding effect of any new anti-cancer therapy that is not a part of the originally assigned treatment.

This secondary estimand will be evaluated for both cohorts and is described by the following attributes:

1. Population:

- Cohort A: Adult participants with locally advanced or metastatic NSCLC without previous systemic treatment for metastatic disease whose tumors harbor a KRAS G12C mutation and a PD-L1 expression < 1%, irrespective of STK11 mutation status.
- Cohort B: Adult participants with locally advanced or metastatic NSCLC without previous systemic treatment for metastatic disease whose tumors harbor a KRAS G12C mutation, a PD-L1 expression ≥ 1%, and an STK11 co-mutation.
- 2. Primary variable: DOR defined as time from the date of first documented response of CR or PR to the date of the first documented progression or death due to any cause, according to RECIST 1.1 assessed by BIRC for participants whose best overall response is CR or PR.

- 3. Treatment of interest: All participants enrolled in this study will be treated with JDQ443 a selective and irreversible KRAS G12C inhibitor administered p.o. 200 mg twice a day continuously.
- 4. Handling of remaining intercurrent events:
 - Treatment discontinuation for any reason: Tumor assessment data collected irrespective of treatment discontinuation will be included to derive DOR (treatment policy strategy).
 - Any public health emergency as declared by local or regional authorities, i.e., pandemic, epidemic or natural disaster: tumor assessment data collected irrespective of such unforeseen events will be considered for the DOR (treatment policy strategy)
 - New anti-cancer therapy: If any new anti-neoplastic therapy is initiated, progression or death occurring after the use of new anti-neoplastic therapy will not be considered and the DOR censored.
- 5. Summary measure: Median duration of response estimated by the Kaplan-Meier method (for cohort A and B, resp.).

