9.4.1.2 Other secondary efficacy endpoints

DCR is defined as the proportion of participants with a BOR of confirmed CR, PR and stable disease (SD) according to RECIST 1.1 (see Appendix 8 Section 10.8). DCR will be assessed by BIRC as well as by local review. DCR and the corresponding 95% confidence intervals based on the exact binomial distribution (Clopper and Pearson 1934) will be presented.

PFS is defined as the time from the date of first dose of study treatment to the date of the first documented progression or death due to any cause. PFS will be assessed by BIRC as well as by local review according to RECIST 1.1 (see Section 10.8 for further details). PFS will be censored if no PFS event is observed before the first to occur between: (i) the analysis cut-off date, and (ii) the date when a new anti-neoplastic therapy is started. The censoring date will be the date of the last adequate tumor assessment prior to cut-off/start of new anti-neoplastic therapy. The PFS distribution will be estimated using the Kaplan-Meier method, and the Kaplan-Meier curves, medians and 95% confidence intervals of the medians will be presented for each cohort.

Time to response (TTR) is defined as the time from the date of first dose of study treatment to the first documented response of either CR or PR, which must be subsequently confirmed (although date of initial response is used, not date of confirmation). CR and PR are based on tumor response data by BIRC as well as per local review and according to RECIST 1.1 (see Section 10.8 for details). All participants in the FAS will be included in TTR calculations. Participants without a confirmed CR or PR will be censored at the study-maximum follow-up time (i.e., LPLV-FPFV) for participants with a PFS event (i.e., disease progression or death due to any cause), or at the date of the last adequate tumor assessment for participants without a PFS event. TTR will be listed and summarized by cohort. The TTR distribution will be estimated using the Kaplan-Meier method, and the Kaplan-Meier curves, medians and 95% confidence intervals of the medians will be presented for each cohort.

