10.8.3.2.10 Sensitivity analyses

This section outlines the possible event and censoring dates for progression, as well as addresses the issues of missing tumor assessments during the study. For instance, if one or more assessment visits are missed prior to the progression event, to what date should the progression event be assigned? And should progression event be ignored if it occurred after a long period of a patient being lost to follow-up? It is important that the protocol and RAP specify the primary analysis in detail with respect to the definition of event and censoring dates and also include a description of one or more sensitivity analyses to be performed.

Based on definitions outlined in Section 10.8.3.2.7and using the draft FDA guideline on endpoints (Clinical Trial Endpoints for the Approval of Cancer and Biologics 2005) as a reference, the following analyses can be considered:

Table 10-12 Options for event dates used in PFS, TTP, duration of response

Situation	Options for end-date (progression or censoring) ¹ (1)= default unless specified differently in the protocol or RAP	Outcome
Α	(1) Date of randomization/start of treatment ³	Censored
В	 (1) Date of progression (2) Date of next scheduled assessment² 	Progressed Progressed
C1	 (1) Date of progression (or death) (2) Date of next scheduled assessment² 	Progressed Progressed
C2	 (1) Date of last adequate assessment² (2) Date of next scheduled assessment² (3) Date of progression (or death) 	Censored Progressed Progressed
D	(1) Date of last adequate assessment	Censored
E	(1) Ignore clinical progression and follow situations above(2) Date of discontinuation (visit date at which clinical progression was determined)	As per above situations Progressed
F	 (1) Ignore the new anticancer therapy and follow the situations above (ITT approach) (2) Date of last adequate assessment prior to new anticancer therapy (3) Date of secondary anticancer therapy(4) Date of secondary anticancer therapy 	As per above situations Censored CensoredEvent
G	(1) Date of last adequate assessment	Censored (only TTP and duration of response)

^{1.} Definitions can be found in Section 10.8.3.2.7

The primary analysis and the sensitivity analyses must be specified in the protocol. Clearly define if and why options (1) are not used for situations C, E and (if applicable) F.

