Situations C (C1 and C2): Progression or death after one or more missing assessments: The primary analysis is usually using options (1) for situations C1 and C2, i.e.

- (C1) taking the actual progression or death date, in the case of only one missing assessment
- (C2) censoring at the date of the last adequate assessment, in the case of two or more consecutive missing assessments

In the case of two or missing assessments (situation C2), option (3) may be considered jointly with option (1) in situation C1 as sensitivity analysis. A variant of this sensitivity analysis consists of backdating the date of event to the next scheduled assessment as proposed with option (2) in situations C1 and C2.

Situation E: Treatment discontinuation due to 'Disease progression' without documented progression: By default, option (1) is used for situation E as participants without documented PD should be followed for progression after discontinuation of treatment. However, option (2) may be used as sensitivity analysis. If progression is claimed based on clinical deterioration instead of tumor assessment by e.g. CT-scan, option (2) may be used for indications with high early progression rate or difficulties to assess the tumor due to clinical deterioration.

^{2.} After the last adequate tumor assessment. "Date of next scheduled assessment" is defined in Section 10.8.3.2.7

^{3.} The rare exception to this is if the patient dies no later than the time of the second scheduled assessment as defined in the protocol in which case this is a PFS event at the date of death

Situation F: New cancer therapy given: the handling of this situation must be specified in detail in the protocol. However, option (1) (ITT) is the recommended approach; events documented after the initiation of new cancer therapy will be considered for the primary analysis i.e. progressions and deaths documented after the initiation of new cancer therapy would be included as events. This will require continued follow-up for progression after the start of the new cancer therapy. In such cases, it is recommended that an additional sensitivity analysis be performed by censoring at last adequate assessment prior to initiation of new cancer therapy.

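### SAP Table 2-6 tells the analyst to ignore new anticancer therapy in the clinical-progression row, where the protocol says to ignore clinical progression; taken literally, it counts DOR and PFS events that the rest of the plan censors

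*SAP*

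**What the plan says.** SAP section 2.7.4 contains the table of outcomes and dates for DOR and PFS. It is captioned Table 2-6, although the surrounding text cites it as Table 2-5. Two adjacent rows matter here.

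- **Stopping treatment for disease progression without documented progression** (the investigator's clinical claim). Date rule: "Ignore the new anticancer therapy and follow situations above". The outcome is left to the rows above.
- **New anticancer therapy before protocol-defined progression.** Date rule: "Date of last adequate assessment prior to start of new anticancer therapy". The outcome is censored.

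The source is protocol Table 10-12 (section 10.8.3.2.10), where these are situations E and F.

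- Situation E, option (1): "Ignore clinical progression and follow situations above". The text below the table confirms the choice: "By default, option (1) is used for situation E as participants without documented PD should be followed for progression after discontinuation of treatment".
- Situation F, option (1): "Ignore the new anticancer therapy and follow the situations above (ITT approach".

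Elsewhere both documents commit this study to censoring at new therapy. The DOR estimand in protocol section 3.2 says "progression or death occurring after the use of new anti-neoplastic therapy will not be considered and the DOR censored", and SAP section 1.2.2 repeats it. SAP section 2.7.3 says "progression or death occurring after the use of new anti-neoplastic therapy will not be considered and the DOR will be censored". For PFS, protocol section 9.4.1.2 names as one of its two censoring limits "ii) the date when a new anti-neoplastic therapy is started". SAP section 2.8.1.4 does the same and adds that clinical deterioration does not count as documented progression.

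**The concern.** The instruction does not fit its row. The row describes situation E and mentions no new therapy, yet the cell carries, almost word for word, option (1) of situation F. It looks like a copying slip, but what it states is a rule, and a wrong one.

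Taken literally, the row tells the programmer to disregard new therapy for anyone who stopped for clinical progression and to use the rows above. The row that censors for new therapy lies below, so the cell does not lead back to it. Progression or death after the new therapy is then an event, provided it falls before two or more assessments have been missed. The DOR estimand excludes exactly that observation.

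The SAP text refers to this table for both DOR and PFS. SAP section 2.7.5 plans no sensitivity analysis for DOR that might expose a wrong implementation.

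**Working it through.** The plan gives no figure to reproduce, so the check compares the texts and then works through one participant.

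**Step 1: compare the rules.**

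| Situation | Protocol Table 10-12, option (1) | Study-specific rule elsewhere | SAP Table 2-6 |
|---|---|---|---|
| E: clinical progression only | Ignore clinical progression | Clinical deterioration is not an event (SAP 2.8.1.4, PFS) | Ignore new therapy |
| F: new therapy | Ignore new therapy (ITT) | Censor (protocol 3.2 and 9.4.1.2; SAP 1.2.2, 2.7.3, 2.8.1.4, 4.5) | Censor at last adequate assessment |

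The F row was adapted to this study. The E row holds neither the protocol's default for E nor the study's choice for F.

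**Step 2: who is affected.** All of these must hold:
- treatment stopped for undocumented progression;
- new anti-neoplastic therapy started, other than protocol-allowed radiotherapy, which SAP 2.7.3 and 2.8.1.4 exempt;
- documented progression or death afterwards, within the interval D2 after the last adequate assessment (SAP 4.5);
- for DOR, a confirmed response.

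**Step 3: one participant.** The dates are assumptions chosen only to show the rule: first PR (later confirmed) at week 6, last adequate assessment at week 24, stop for clinical progression at week 26, new therapy at week 27, progression by BIRC at week 30.

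Inputs from the documents:
- Time to event = end date − start date + 1 (protocol 10.8.4.5.1).
- Months = days / 30.4375 (SAP 2.1.3.6).
- The last adequate assessment is before week 45, so D2 = 2 × 6 + 2 = 14 weeks (SAP 4.5, Rule 1).

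Study day = 7 × week + 1, so week 6 is day 43, week 24 is day 169 and week 30 is day 211. From week 24 to week 30 is 6 weeks, less than 14, so the missing-assessment rule does not censor the event.

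| | Literal cell | Next row, estimand and PFS rule |
|---|---|---|
| DOR | 211 − 43 + 1 = 169 days (5.6 months), **event** | 169 − 43 + 1 = 127 days (4.2 months), **censored** |
| PFS | 211 − 1 + 1 = 211 days (6.9 months), **event** | 169 − 1 + 1 = 169 days (5.6 months), **censored** |

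Both status and date change. Moving the first PR to week 12 (day 85) gives the same pattern for DOR: an event at 211 − 85 + 1 = 127 days against censoring at 169 − 85 + 1 = 85 days. PFS is unchanged by that move.

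**Step 4: effect on the medians.** This cannot be computed. Neither document gives an expected rate of clinical progression followed by new therapy.

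**The case against.** The strongest reply is that the table does not plainly order an event to be counted. The next row also covers this participant, because clinical progression is not protocol-defined progression and the new therapy therefore preceded it. On that view two rows conflict, and everything else settles the conflict in favour of censoring: the estimand, SAP 2.7.3 and 2.8.1.4, and SAP 4.5, which lists new anticancer therapy as a PFS censoring reason without exception. This stands as far as intent goes; a careful reader can recover it. It does not make the cell right. The table states no precedence, and the cell points only to the rows above it.

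A second reply is that the post-progression scan may not exist. Protocol Table 8-1 continues post-treatment imaging for participants whose end-of-treatment reason is something other than disease progression, and this group's recorded reason is disease progression. That makes the week-30 scan in the example less certain. However, protocol 7.1.2 continues efficacy follow-up when progression has not been documented, and protocol 8.4.1 continues it even after new therapy. Death within D2 needs no scan.

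A third is that the appendix recommends the ITT option for situation F. The appendix also requires the protocol to specify how new therapy is handled, and sections 3.2 and 9.4.1.2 choose censoring.

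A fourth is that the numbers will be small. This is accepted. Protocol 10.8.4.4 reserves this discontinuation reason for documented symptomatic deterioration, and protocol 8.4.1 asks sites to continue treatment, where clinically acceptable, when BIRC does not confirm progression. DOR and PFS are also estimated descriptively, without a test.

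**Conclusion.** The cell is wrong as written. It replaces the protocol's rule for clinical progression with a rule for new therapy that this study did not adopt, and it contradicts the next row, the DOR estimand and the PFS censoring rules.

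The consequence is confined to DOR and PFS, in the few participants who meet every condition in Step 2. For such a participant a censored time becomes a later event. No shift in a median is claimed, and the worked dates are illustrative. The conclusion rests only on the wording of the two tables and the study-specific censoring rules. The correction should be made because this is the table the SAP cites for a key secondary endpoint, and the choice should not fall to whoever programs it.

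**What to change.** In SAP Table 2-6, change the date cell of the clinical-progression row so that it says to ignore clinical progression and follow the other situations in the table. Referring to the other situations, and not only those above, keeps the new-therapy row in force for these participants.

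No separate precedence statement is needed. If one is added, it should carry the exemption for protocol-allowed radiotherapy, which the new-therapy row itself omits; otherwise it could be read as censoring participants who received exempt radiotherapy.

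The cost is one table cell. No new data or analysis is required, and the change only restores what the protocol and the rest of the SAP already state.
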